9.8. Concomitant Medications

All prescription and non-prescription medications and therapies, including pharmacologic doses of vitamins, herbal medicines, or other non-traditional medicines, taken from 28 days prior to the first dose of TVB-2640 through the Final Study Visit must be recorded in the eCRF.

9.8.1. Excluded Medications

The following medications and treatments are prohibited during study participation.

- Any investigational agent or device other than TVB-2640.
- Strong inhibitors or inducers of cytochrome P450 3A4 (CYP3A4). (Refer to the following for examples:
<http://www.fda.gov/drugs/developmentapprovalprocess/developmentresources/druginteractionslabeling/ucm093664.htm>.)
- Drugs historically associated with NAFLD (amiodarone, methotrexate, systemic glucocorticoids, tetracyclines, tamoxifen, estrogens at doses greater than those used for hormone replacement, anabolic steroids, valproic acid, and other known hepatotoxins).
- Glucagon-like peptide analogue or a complex oral OAD regimen (3 or more OADs).
- Insulin dose adjustment >10%. (Subjects receiving insulin at baseline who require a >10% dose adjustment for the management of Type 2 diabetes mellitus are to be discontinued from the study.)

- Introduction of new or changes in continuing oral diabetic medications (e.g., pioglitazone) is prohibited. Concomitant oral diabetic medications are permitted only if the dose has been stable for at least 3 months before screening and remains stable throughout study participation.

Subjects requiring such treatment during study participation are to be discontinued.

9.8.2. Permitted Medications

Medications and treatments other than those specified in [Section 9.8.1](#) are permitted during the study. Subjects should be closely monitored, and treatment is to be instituted for disease-related symptoms, as appropriate.

9.8.3. Contraception

[REDACTED]
[REDACTED]
[REDACTED] females of childbearing potential must use two forms of birth control, one being a barrier method (i.e., condoms, diaphragm, non-hormonal IUD) throughout the study and for at least 3 months after the final study drug dose. Hormonal contraception (estrogens stable ≥ 3 months) and hormonal IUDs are permitted if used with a secondary barrier birth control method (e.g., condoms).

9.9. Blinding

In Cohorts 1 and 2, study drug will be dispensed to subjects in a single-blinded fashion. All other study personnel, with the exception of personnel conducting/interpreting imaging studies (see [Section 11.1](#)) at each study center, will be unblinded to the subject's treatment assignment. In Cohort 3, TVB-2640 will be dispensed in an open-label fashion.

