5.1. TVB-2640

The clinical safety profile to date for TVB-2640 is based primarily on one completed uncontrolled open-label Phase 1 study in humans (Study 3V2640-CLIN-002) in 136 patients with solid tumors, 76 treated with monotherapy (at doses ranging from 60 mg/m² to a dose of 240 mg/m² (i.e., up to 600 mg) and 60 treated with TVB-2640 in combination with a taxane (paclitaxel or docetaxel).

Overall, TVB-2640 demonstrated a favorable tolerability profile. Most treatment-emergent adverse events (TEAEs) were Grade 1 or 2 in intensity, non-serious, and manageable.

As anticipated, based on nonclinical study findings, the principal toxicities associated with TVB-2640 as monotherapy were skin and ocular effects. With monotherapy, most skin events were Grade 1 or 2 in intensity, and all were non-serious.

The maximum tolerated dose (MTD) of TVB-2640 monotherapy in patients with solid tumors was determined to be 100 mg/m². Dose-limiting toxicities (DLTs) associated with TVB-2640 monotherapy were skin and ocular events, including corneal edema, keratitis, and palmar-plantar erythrodysesthesia (PPE) syndrome.

As monotherapy, the most common individual TEAEs were alopecia (61%), PPE syndrome (46%), fatigue (37%), decreased appetite (26%), and dry skin (22%).

When TVB-2640 was administered in combination with a taxane (paclitaxel or docetaxel), skin and ocular effects also were common. Most skin events were Grade 1 or 2 in intensity, and all but 1 skin event were non-serious.

As was the case with monotherapy, the MTD of TVB-2640 in combination with paclitaxel was determined to be 100 mg/m². DLTs associated with TVB-2640 in combination included PPE syndrome and uveitis. The most common TEAEs with TVB-2640 in combination with paclitaxel were fatigue (53%), alopecia (46%), PPE syndrome (46%), nausea (40%), and peripheral neuropathy (36%). Peripheral neuropathy is known to be associated with paclitaxel.

When TVB-2640 was administered in combination with paclitaxel, 6 episodes of serious pneumonitis were experienced by 5 patients, with all assessed by the Investigator as related to both TVB-2640 and paclitaxel. (No cases of pneumonitis were reported among monotherapy patients.) Given the occurrence of these events, respiratory events were identified as adverse events of special interest for patients receiving TVB-2640 in combination.

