6.4.2. Safety Endpoints

Safety endpoints are:

- Proportion of subjects experiencing treatment-emergent adverse events (TEAEs), Grade 3 or 4 TEAEs, and serious adverse events (SAEs).
- Change from baseline in vital sign measurements, 12-lead electrocardiogram (ECG) findings, and clinical laboratory test results.
- Proportion of subjects experiencing treatment-emergent ophthalmologic abnormalities.

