11. EFFICACY, PHARMACOKINETIC, AND PHARMACODYNAMIC ASSESSMENTS

11.1. Efficacy and Pharmacodynamic Assessments

11.1.1. Magnetic Resonance Imaging Studies

All imaging studies will be done by experienced research personnel according to a standard imaging protocol. Personnel reading imaging studies will be blinded to the subject's treatment group allocation and clinical and biochemical data. A trained image analyst will assess all images at each study center; ideally, the same reviewer should review all scans at that study center for the duration of the study. All imaging studies also will be read centrally; the central reader also will be blinded to the subject's treatment group allocation and will not have access to the subject's clinical and biochemical data. The results of the central read will be used in the analysis of imaging data.

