11.1.2. Liver Fibrosis by FibroScan

The degree of liver fibrosis, as indicated by the kpa, will be assessed using Fibroscan at the time points designated in Table 2.

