12.1.4. Ophthalmologic Examinations

Ophthalmologic examinations are to be performed for all subjects at the time points designated in [Table 2](#).

Near and far visual acuity is to be assessed by an ophthalmologist using standard measures (e.g., Early Treatment Diabetic Retinopathy Study or similar) in each eye. If the subject wears corrective lenses (e.g., glasses), then visual acuity is to be checked first with corrective lenses and then without correction. (A best-corrected examination is not required.) Note that contact lens wearers are to abstain from contact lens use during study drug treatment.

A slit lamp examination (biomicroscopy), including examination of the eyelids, conjunctiva, cornea, anterior chamber, iris, and lens, is to be performed after completion of visual acuity testing for the determination of corneal health.

If a subject experiences a treatment-emergent ophthalmologic abnormality, an ophthalmologic examination should be performed within 24 to 48 hours or next business day after symptom onset to evaluate the abnormality.

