3.2. Randomization and Blinding

Subjects who are candidates for enrollment into the study will be assigned a sequential and unique subject number by the Investigator after the subject has provided written informed consent. Once a subject number has been assigned, it cannot be reused.

Subjects who have provided written informed consent will be evaluated for eligibility by the Investigator to ensure that the entry criteria (see Protocol Sections 8.2 and 8.3) have been satisfied and that the subjects is eligible for participation in this clinical study.

Two TVB-2640 dose levels are planned to be evaluated in a sequential fashion: 25 mg and, if study suspension criteria are not met at the 25 mg dose level (see Protocol Section 7.2), 50 mg. At each dose level, subjects will be randomly assigned to TVB-2640 or placebo at a 2:1 ratio, with randomization stratified by type 2 diabetes mellitus (DM) status. The 50 mg dose level will also be stratified by country:

- 25 mg dose level: TVB-2640 (Planned N=30) and Placebo (Planned N=15)
- 50 mg dose level: US: TVB-2640 (Planned N=30) and Placebo (Planned N=15); China: TVB-2640 (Planned N=18) and Placebo (Planned N=9); Total: TVB-2640 (Planned N=48) and Placebo (Planned N=24)

Randomization will be done via Interactive Web Response System (IWRS). Subjects are to receive their first study drug dose on Day 1 within 24 hours after randomization.

At both dose levels, subjects will receive TVB-2640 or placebo QD PO for 12 weeks.

Study drug will be dispensed to subjects in a single-blinded fashion. All other study personnel, with the exception of personnel conducting/interpreting imaging studies (see Protocol Section 11.1) at each study center, will be unblinded to the subject's treatment assignment.

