8.6.3. Ophthalmologic Examinations

The proportion of subjects experiencing ophthalmologic abnormalities will be tabulated by visit and by treatment group. The clinical interpretation of the ophthalmologic examination will be tabulated as normal or abnormal. The worst-case post-baseline will also be summarized.

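### The blinding rule does not mask the eye examiner, which leaves the active-versus-placebo comparison of ocular abnormalities open to detection bias

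*Protocol*

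**What the plan says.** Protocol Section 9.9 sets the rule for Cohorts 1 and 2. Subjects are blinded, while "All other study personnel, with the exception of personnel conducting/interpreting imaging studies" at each centre are to be unblinded to assignment. The Synopsis (Methodology) and Section 7.1 repeat this. SAP Section 3.2 does too: "Study drug will be dispensed to subjects in a single-blinded fashion", followed by the same single exception.

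The exception points to Protocol Section 11.1. Section 11.1.1 says "Personnel reading imaging studies will be blinded" to allocation and to clinical and biochemical data, and adds a blinded central read that is used for analysis.

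Eye examinations are in Section 12.1.4, outside Section 11.1. There, "Near and far visual acuity is to be assessed by an ophthalmologist using standard measures". A slit-lamp examination follows, with no examiner named. Masking is mentioned for neither.

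The results feed one of three safety endpoints in Section 6.4.2: "Proportion of subjects experiencing treatment-emergent ophthalmologic abnormalities". SAP Section 8.6.3 describes the scoring: "The clinical interpretation of the ophthalmologic examination will be tabulated as normal or abnormal". It is tabulated by visit and treatment group, with a worst post-baseline summary.

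Safety versus placebo is a primary objective (Section 6.1). On what is already known of the drug, Section 5.1 states "Dose-limiting toxicities (DLTs) associated with TVB-2640 monotherapy were skin and ocular events". That experience comes from patients with solid tumours.

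**The concern.** Three features together create the usual conditions for detection bias: the outcome is a judgement rather than an instrument reading, the toxicity is expected, and nothing prevents the assessor from knowing the arm. An examiner who expects corneal or dry-eye findings on active drug may call borderline findings abnormal more often in active subjects. One who is keen to discount them may do the reverse.

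At stake is the interpretation of the ocular safety table. The placebo arm helps to separate drug effect from background eye findings only if both arms are judged by the same standard. Section 9.7 says the adverse event profile will inform dose optimisation in later studies, so the result will be used beyond this trial. With about 30 subjects per active arm in the US and no formal test, readers will judge the raw difference between arms.

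**Working it through.** **Step 1: does any text mask the eye examiner?**

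| Place | What it covers | Eye examiner masked? |
|---|---|---|
| Protocol Synopsis, 7.1 and 9.9; SAP 3.2 | All study personnel unblinded except imaging staff | No |
| Protocol 11.1.1 | Local and central imaging readers blinded | Not covered |
| Protocol 12.1.4 | Acuity and slit-lamp procedures | Silent |
| SAP 8.6.3 | Normal/abnormal tabulation, worst case | Silent; no masked review |

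The gap results from a stated rule with one exception, not from a missing detail.

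**Step 2: does the examiner need the assignment?** Neither document says so. The ocular withdrawal text in Protocol Section 8.6 is written in terms of study drug, without reference to arm. Section 7.2 gives the Safety Review Committee its own access to unblinded data.

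**Step 3: the plan's only numerical safety statement.** Protocol Section 13.1 claims at least a 95% chance of seeing one or more adverse events with 30 subjects at a 10% rate. Check: 1 - 0.9^30 = 0.9576, so the claim holds. It concerns detection within one arm and says nothing about a fair comparison between arms.

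**Step 4: what differential judgement could do (illustration only).** The documents give no ocular abnormality rate for this population and no misclassification rates, so every input here is assumed. The true rate t is the same in both arms, so there is no drug effect.

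Observed rate = t × sensitivity + (1 - t) × false-positive rate

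Worked case, with t = 10%, sensitivity 90% active and 80% placebo, false-positive rate 10% active and 5% placebo:

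- Active: 0.10 × 0.90 + 0.90 × 0.10 = 0.180
- Placebo: 0.10 × 0.80 + 0.90 × 0.05 = 0.125
- Spurious difference: +5.5 points

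| Sensitivity, active / placebo | False positive, active / placebo | t = 5% | t = 10% | t = 20% |
|---|---|---|---|---|
| 90% / 90% | 5% / 5% | 0 | 0 | 0 |
| 90% / 80% | 10% / 5% | +5.25 | +5.5 | +6.0 |
| 95% / 75% | 15% / 5% | +10.5 | +11.0 | +12.0 |
| 75% / 90% | 2% / 5% | -3.6 | -4.2 | -5.4 |

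(Differences are in percentage points, active minus placebo.)

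**Step 5: accumulation over visits.** Protocol Table 2 schedules four post-baseline eye examinations for a completer (Weeks 4, 8, 12 and 16), and the SAP also reports the worst case. Assume false-positive rates of 2% and 5% per examination, with visits independent. The worst-case rates are then 1 - 0.98^4 = 7.8% and 1 - 0.95^4 = 18.5%. Small differences per visit can widen in that summary. Correlated visits would widen them less.

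**The case against.** **Single-blinding is declared, and safety is descriptive.** Both are true. Protocol Section 13.2.3 and SAP Section 8.5 rule out formal safety testing, and the primary endpoint has blinded readers. No error rate depends on the ocular table. This limits the consequence but does not make the comparison fair.

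**Ascertainment is structured.** Both arms have the same scheduled visits, listed eye structures and standard acuity measures. Subjects are blinded, which helps to protect symptom reports and effort-dependent acuity. This stands, but the normal/abnormal call remains a judgement.

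**A reader might infer that the ophthalmologist examined subjects knowing their arm.** The documents do not establish that. It follows only if the ophthalmologist counts as study personnel at the centre, and an outside consultant might be unaware. An ophthalmologist is named for acuity and for eligibility, but nobody is named for the on-study slit-lamp examination or the final call. What the text supports is that masking is not provided for.

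**A reader might extend the point to FibroScan and the VCTE endpoint.** Section 11.1.2 says "The degree of liver fibrosis, as indicated by the kpa, will be assessed using Fibroscan" and is silent on blinding. However, Section 9.9 cross-refers to Section 11.1 as a whole, which includes 11.1.2. The FibroScan baseline cell in Table 2 also carries footnote 16, which concerns baseline imaging studies. On the natural reading, the operator is inside the exception.

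**A reader might also infer that the 25 mg versus 50 mg comparison is compromised.** That is weakly supported. Both are active arms with the same examiner knowledge, so much of any expectation effect would be shared. The cohorts are also sequential, so masking assignment would not hide the dose level.

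**Little remains to be changed.** This is partly right. Table 2 footnote 2 reports the 25 mg cohort complete and the 50 mg cohort fully enrolled but ongoing. SAP Section 3.5 describes China enrolment as delayed and uncertain. Masking can help only the examinations still to come.

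**Conclusion.** The point holds in a limited form. The plan's blinding rule makes no provision for masking the eye examiner, so the active-versus-placebo comparison of treatment-emergent ophthalmologic abnormalities is open to detection bias. This affects estimation and interpretation, not Type I error.

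Size and direction are unknown. The range of -5.4 to +12 points comes wholly from assumed inputs and must not be read as an estimate for this trial. The conclusion assumes that eye examiners fall under the general rule for study personnel. If they were in fact kept unaware, the documents should say so, and the concern would then fall away for those examinations.

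Masking the examiner would also not remove every source of differential ascertainment. Unblinded site staff still record adverse events and can prompt the symptom-driven examinations in Protocol Section 12.1.4.

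**What to change.** - Extend the exception in Protocol Section 9.9 to personnel who conduct or interpret ophthalmologic examinations as well as imaging studies. Make the same change in the Synopsis, Section 7.1 and SAP Section 3.2.
- Leave treatment assignment off ophthalmology referral and report forms unless it is needed to manage an event.
- Apply both changes to all eye examinations still to be done in randomised Cohort 2 subjects, including those in China. Cohort 3 is open-label and is not affected.
- State in the safety tables that masking of the eye examiner was not required for earlier examinations. That wording is accurate without claiming that examiners knew the arm.

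The cost is one clause in four places, a revised form and a table footnote. The same examiners do the same examinations, so no reader, visit or procedure is added and no sample size figure changes. The downside is an occasional unblinding step when an individual event needs it.

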10. BASELINE ASSESSMENTS

All subjects must provide written informed consent before the performance of any study-related procedures.

10.1. Demographics

Subject demographics, including age, sex, race, and ethnicity, are to be documented during screening.

10.2. Medical and Social History

A complete medical history is to be documented during screening and updated at baseline, prior to administration of the first study drug dose.

The medical history also is to include NASH related history, including the date of diagnosis, and as available, NAS score, APRI, NAFLD fibrosis score, and/or enhanced liver function (ELF) score, as well as abbreviated weight history, family history (siblings and subjects; particularly of obesity and liver disease), past medical/surgical events and illness history (including diabetes, gestational diabetes, hypertension, lipodystrophy, polycystic ovarian syndrome, and any history of Gilbert's disease) and other associated co-morbid conditions including previously diagnosed lipid and metabolic disease-related conditions (hypercholesterolemia, hypertriglyceridemia, diabetes mellitus), and all diagnoses related to previous liver disease as well as other diagnoses of major organ systems including cardiac disease, renal disease, endocrine disease, hypertension, gout or other arthropathies, disturbances of vision, peripheral neuropathy, myopathy, pancreatitis, and cholelithiasis.

History of previous COVID-19 infection or vaccination against SARS-CoV-2 should also be documented.

Social history, including alcohol, tobacco, and caffeine use, also will be documented.

10.3. Screening Serology

Screening serologies include HIV RNA, HBsAg, anti-HCV, and HCV RNA. A PCR test for SARS-CoV-2 (the virus that causes COVID-19) also is to be performed.

Subjects with positive anti-HCV who test negative for HCV RNA at screening will be allowed to participate in the study.

10.4. Pregnancy Testing

For women of child-bearing potential, a serum β -hCG pregnancy test will be performed during screening and a serum or urine β -hCG pregnancy test will be performed within 48 hours before baseline. Results must be available and confirmed to be negative before the subject is eligible for randomization in the study. Pregnancy testing is to be repeated during the study any time pregnancy is suspected.

All subjects of reproductive potential must agree to adequate birth control from the time the screening pregnancy test is performed through 3 months after the final study drug dose.

Study drug is to be discontinued for any subject with positive pregnancy test findings; see [Section 12.2.6](#) for details regarding management of any pregnancies during the study.

Women of non-child-bearing potential are to have this documented as part of the medical history.

11. EFFICACY, PHARMACOKINETIC, AND PHARMACODYNAMIC ASSESSMENTS

11.1. Efficacy and Pharmacodynamic Assessments

11.1.1. Magnetic Resonance Imaging Studies

All imaging studies will be done by experienced research personnel according to a standard imaging protocol. Personnel reading imaging studies will be blinded to the subject's treatment group allocation and clinical and biochemical data. A trained image analyst will assess all images at each study center; ideally, the same reviewer should review all scans at that study center for the duration of the study. All imaging studies also will be read centrally; the central reader also will be blinded to the subject's treatment group allocation and will not have access to the subject's clinical and biochemical data. The results of the central read will be used in the analysis of imaging data.

11.1.1.1. Proton-density Fat Fraction by Magnetic Resonance Imaging (MRI-PDFF)

MRI-PDFF is a non-invasive, quantitative, and accurate measure of liver fat content to assess treatment response in early-phase of NASH studies (Caussy 2018). MRI-PDFF is to be determined at the time points designated in Table 2. Visceral adipose tissue measurement by MRI will be performed for all eligible subjects. Subjects who are randomized will have repeat visceral adipose tissue and liver fat measurements performed.

11.1.1.2. Liver Stiffness by Magnetic Resonance Elastography

MRE has been shown to be a robust, accurate biomarker for the quantitative, noninvasive evaluation of liver stiffness as a surrogate for liver fibrosis and for NASH detection. MRE is to be determined during screening, as per Table 2. Note that subjects without a biopsy performed within 24 months of randomization MUST have MRE performed during screening.

11.1.2. Liver Fibrosis by FibroScan

The degree of liver fibrosis, as indicated by the kpa, will be assessed using Fibroscan at the time points designated in Table 2.

11.1.3. Clinical Laboratory Tests

Refer to the Laboratory Manual for details regarding clinical efficacy/pharmacodynamic laboratory sample collection, processing, storage, and shipment. Note that in Cohort 3 (75 mg), some of the exploratory biomarker samples will not be collected or may be collected on an optional basis, as indicated in Table 2.

